7.1. Time and Events Table

Procedure	Pre-Screen 1	Screen 2	In-Patient Period ^{3,4}							Out-patient Visits ^{4,5}													
			Day -1	Day 1			Day 2	Day 3	Day 4	Week													
				Pre-dose	0	2 h	8 h	24 h	48 h	72 h	NA	1	2	4	8	12	18	24	26	32 ⁵	36 ⁵	40 ⁵	
				5	8	15	29	57	85	127	169	183	225 ⁵	253 ⁵	281 ⁵	Day							
Haematology (including blood eosinophil count), Clin. Chem., Urinalysis and hsCRP		X	X					X	X	X	X	X	X	X	X	X	X	X	X	X	X	X	
Serum save (for immunological analysis, if needed)		X																					
Inflammatory markers		X																					
Complement (C3 & C4)		X	X					X	X	X	X	X	X	X	X	X	X	X	X	X	X	X	
Total IgE			X					X	X	X	X		X	X	X	X	X	X	X	X	X	X	
PK Blood Samples																							
Immunogenicity				X									X	X	X	X	X	X	X	X	X	X	
CICs				X				X					X	X	X	X	X	X	X	X	X	X	
12-lead ECG ¹⁴		X	X	X		X	X	X	X	X	X	X	X	X	X	X	X	X	X	X	X	X	
Vital signs ¹⁵		X	X	X		X	X	X	X	X	X	X	X	X	X	X	X	X	X	X	X	X	
AE/SAE review (inc local ISR up to 72 h after dosing)				X	¹⁶																		
IL-5 sample			X										X	X		X	X	X	X	X	X	X	
Exploratory biomarkers of asthma in blood			X												X			X					
Spirometry		X	X			X		X		X		X		X		X				X	X	X	
PEF Training ¹⁷		X																					
PEF ¹⁷													X	¹⁷									
Diary review ¹⁷													X	X	X	X	X	X	X	X	X	X	

Abbreviations: ACT = Asthma Control Test; AE = adverse event; BMI = body mass index; CICs = circulating immune complexes; CRP = C-reactive protein; ECG = electrocardiogram; FSH = follicle stimulating hormone; h = hour(s); Hep B = Hepatitis B; Hep C = Hepatitis C; HIV = human immunodeficiency virus; IgE = immunoglobulin E; IL-5 = interleukin-5; IP = Investigational Product; ISR = injection site reactions; PEF = peak expiratory flow; PK = pharmacokinetic; SABA = short acting β -agonist; SAE = serious adverse event.

Notes:

1. Pre-screen up to 12 weeks before dosing. Blood eosinophils must be ≥ 200 cells/ μ L for participants to proceed to screening. Blood eosinophil count may be existing data or obtained at a pre-screen visit.
2. Screening up to 4 weeks before randomisation. Screening procedures may be done at one or more visits, within the screening window.
3. In the UK, all participants will be in-patient for at least 72 h after dosing. In Germany, all participants will be in-patient for at least 8 days after dosing (see [Appendix 8](#) for the German-specific time and events table).
4. Allowed time deviations will be documented in the Study Reference Manual.
5. All participants will have all out-patient visits up to Week 26 after dosing. Each cohort will also have out-patient visits after week 26, depending on the dose, as follows:
 - 2 and 10 mg: Week 32 only
 - 30 mg and 100 mg: Week 36 only
 - 300 mg: Weeks 32 and 40

(For unplanned dose levels, the timing of out-patient visits will be documented in a Note to File.)

6. Informed consent will be taken either at the pre-screen visit, for participants who don't have an existing eosinophil count, or at screening, for those who do.
7. Blood eosinophils will be included in the haematology panel at all time points other than the pre-screen visit.
8. If required to confirm postmenopausal status.
9. Women on hormone replacement therapy, whose post-menopausal status cannot be confirmed, only.
10. Including cardiovascular (CV) disease, asthma exacerbation, and drug, alcohol and smoking history.
11. If the participant consents, an optional, genetic sample will be collected once during the study.
12. At each applicable visit, ACT should be done before any other assessment.
13. Height at pre-screening or screening only.
14. ECGs triplicate at all time points. ECGs should be time-matched to baseline (i.e. pre-dose on Day 1) from Day 2 onwards.
15. Blood pressure and heart rate in triplicate before dosing; single measurements after dosing. Single temperature and respiratory rate measurements at all time points.
16. Only SAEs are collected before dosing (see Section [7.3.1](#)).
17. PEF will be recorded in the evening before bedtime on the day of the screening visit, then **twice each day (once in the morning upon waking and once in the evening before bedtime)** from the day after screening until the end of the study. Training of the participant in how to take measurements will occur at screening. PEF measurements will be taken and results will be recorded by the site while the participant is in-patient at the clinical site (ie from the evening of Day -1 until the morning of discharge). At all other time points, the participant will record their PEF as instructed, on their diary card, along with any rescue medication use and adverse events. Site staff will review the diary cards at each out-patient visit.

Table 4 Pharmacokinetic sampling time points

Dose level	Pre-dose	Post-dose															
		Hours				Days											
		2	8	24	48	5	8	15	29	57	85	127	169	183	225	253	281
2 mg and 10 mg	X	X	X	X	X	X	X	X	X	X	X	X	X	X			
30 mg and 100 mg	X	X	X	X	X	X	X	X	X	X	X	X	X	X	X	X	
300 mg	X	X	X	X	X	X	X	X	X	X	X	X	X	X	X	X	X

Notes: For unplanned dose levels, PK sampling time points will be documented in a Note to File.

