4.2. Treatment Arms and Duration

- Cohorts: Planned cohort sizes are as follows:
 - *Cohorts 1 (2 mg), 2 (10 mg) and 5 (300 mg)*: 8 participants per cohort – 6 receiving GSK3511294 and 2 receiving placebo
 - *Cohorts 3 (30 mg) and 4 (100 mg)*: 12 participants per cohort – 9 receiving GSK3511294 and 3 receiving placebo
- The dose levels, number of cohorts and number of participants per cohort may be adjusted during the course of the study to achieve study objectives based on emerging data from the ongoing analysis. The ratio of active to placebo participants in each cohort will be 3:1.
- Blood eosinophils pre-screen and screening: It is anticipated that a high proportion of the defined asthma population may have blood eosinophil levels that do not meet the inclusion criteria of ≥ 200 eosinophil cells/ μL , therefore a blood eosinophils pre-screen assessment will be performed. Participants are eligible to skip the blood eosinophils pre-screening visit and go directly to the screening visit, if they have a documented blood test result within 12 weeks before dosing demonstrating a blood eosinophil level ≥ 200 cells/ μL . If blood eosinophil levels within the prior 12 weeks are not available, participants will provide written informed consent at a pre-screening visit followed by a pre-screen assessment of blood eosinophil level. Participants who fulfil the pre-screening criteria will then attend the clinic for a full screening visit. Blood eosinophil level will be measured at screening to confirm eligibility.
- In-patient period: Participants will be admitted the day before dosing, and the minimum post dose in-patient period for all participants will be 72 hours in the UK and 8 days in Germany ([Appendix 8](#)). Participants will be monitored for local injection site reactions and allergic reactions for at least 72 hours post dose. In the case of such reactions, appropriate medical treatment will be administered. Participants will be discharged only if the Investigator deems it safe for the participant to leave the unit (For further information regarding the in-patient period in Germany, please refer to Section [12.8.2](#)).

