
 ▪ Duration of the study 	
 ▪ Final follow-up at all dose levels is scheduled to exceed 5 terminal $t_{1/2}$ of GSK3511294 (predicted $t_{1/2}$ is about 37 days; shortest time to follow-up after dosing is 225 days). Owing to the increased affinity of GSK3511294 for IL-5, blood eosinophils levels may still be reduced at the final scheduled follow-up visit, particularly at higher dose levels. However, reduction in blood eosinophils is not considered to be a safety concern – residual levels of blood eosinophils are expected to be present, and there have been no safety signal from chronic dosing with mepolizumab, reslizumab or benralizumab. 	
 ▪ Follow-up will be extended in any participant for whom there are safety concerns, until that concern is discharged.

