9.3.2. Interim Analyses

In stream data review will occur during the study to support dose escalation decisions, and formal interim analyses are planned to ensure accumulated safety, PK and PD data are deemed sufficient to determine the doses and dosing interval to move forward into the next phase of development but is not expected to affect the progression of this FTIH study.

Currently, the first interim analysis is projected to occur once data is available at the 12-week time point after dosing in Cohort 4 (planned 100 mg dose). The primary focus of this interim analysis will be reduction in blood eosinophil counts. The ratio to baseline will be derived for each dose and time point and will be compared to corresponding data from the placebo arm. Posterior means and corresponding 95% credible intervals will be constructed for each of the available doses and time points. Furthermore, posterior probabilities that the placebo adjusted ratio is less than various thresholds of interest will be constructed.

The earliest next interim analysis is planned no earlier than once data is available at the 26-week time point after dosing Cohort 4 (planned 100 mg dose). The primary focus of

this and potential subsequent interim analyses will be the same as the first interim analysis (described above).

The interim analyses will be performed by GSK Clinical Statistics and only the responsible statistician (and Quality control [QC] statistician) and the CPMS representative will have access to individual participant data. However, the findings of the interim analyses will be shared with the entire GSK study team.

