9.4.2.3. Blood eosinophil count

Blood eosinophil count will be log transformed prior to analysis and the ratio to baseline for each dose and time point will be summarised using appropriate descriptive statistics and will be compared to corresponding data from the placebo arm. The primary intent will be to analyse this data by fitting a Bayesian dose response model. The 4-parameter Emax model will be fitted by first intent; however, should the data not allow for a suitable model fit, then other models may be attempted. Posterior means and corresponding 95% credible intervals will be constructed for each dose and time point. Furthermore, posterior probabilities that the placebo adjusted ratio is less than various thresholds of interest will be constructed.

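### Does the staggered visit schedule after Week 26 undermine the Emax analysis of late eosinophil counts?

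*Protocol*

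**What the plan says.** Section 7.1, footnote 5, gives every cohort all visits up to Week 26. Beyond that the 2 and 10 mg cohorts have Week 32 alone, the middle doses have "30 mg and 100 mg: Week 36 only", and the top dose has "300 mg: Weeks 32 and 40". The German schedule in Section 12.8.2.1 repeats this. Section 4.2 explains that follow-up length depends on dose because it follows the predicted eosinophil profile, and that it may be adjusted.

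Section 4.2 also sets cohort sizes. The 2, 10 and 300 mg cohorts each have "6 receiving GSK3511294 and 2 receiving placebo"; the 30 and 100 mg cohorts each have 9 active and 3 placebo.

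For eosinophils, Section 9.4.2.3 states that "The 4-parameter Emax model will be fitted by first intent" and that "Posterior means and corresponding 95% credible intervals will be constructed for each dose and time point". It allows other models if the fit is unsuitable. Section 9.3.2 uses the same approach at the interim analyses: "The ratio to baseline will be derived for each dose and time point and will be compared to corresponding data from the placebo arm". Neither section says whether the model is fitted visit by visit or jointly over time. Section 9.3 leaves full analysis details to the Reporting and Analysis Plan.

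**The concern.** A 4-parameter Emax curve has no time term, so output by dose and time point suggests a separate fit at each visit. After Week 26 no visit contains all doses, and 100 mg and 300 mg never meet again. Read that way, the model has more parameters than dose levels at Weeks 36 and 40, and its posteriors might simply return the prior. The placebo comparison also thins out, because placebo participants follow their own cohort's schedule.

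The late phase matters to the sponsor. Section 4.7.1 accepts that "blood eosinophils levels may still be reduced at the final scheduled follow-up visit, particularly at higher dose levels", and the rationale for Amendment 6 is to see how counts return towards baseline at the highest doses. If the late estimates were artefacts of the prior, the choice of dosing interval for the next phase could be misinformed.

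**Working it through.** **Inputs.** Cohort sizes come from Section 4.2 and visits from Section 7.1, footnote 5. Planned sizes are used, without dropout. The cohorts sum to 8 + 8 + 12 + 12 + 8 = 48, which matches the planned sample size, with 2 + 2 + 3 + 3 + 2 = 12 on placebo. The SD of the log ratio to baseline is not in the protocol; 0.5 is assumed, with 0.4 to 0.6 as the range.

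**Step 1: what each visit contains.** The rank is that of the Jacobian of E0 + Emax·d^h/(ED50^h + d^h) at the doses present.

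| Visit | Doses (mg) | Levels incl. placebo | Placebo n | Rank (of 4) |
|---|---|---|---|---|
| Week 26 | 2, 10, 30, 100, 300 | 6 | 12 | 4 |
| Week 32 | 2, 10, 300 | 4 | 2+2+2 = 6 | 4 |
| Week 36 | 30, 100 | 3 | 3+3 = 6 | 3 |
| Week 40 | 300 | 2 | 2 | 2 |

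Four parameters cannot all be learned from Week 36 or Week 40 alone. Week 32 is just identified, with nothing left to test fit.

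**Step 2: what that costs.** At Weeks 36 and 40 the rank equals the number of levels, so the model can still move each observed mean freely (at Week 36, as long as the means are ordered with dose). The means at the doses present, and their contrasts with placebo, are informed by data.

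An illustration at Week 36, with assumed ratios of 1.0, 0.5 and 0.3 at placebo, 30 and 100 mg on the log scale:

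| Hill slope | ED50 (mg) | Ratio at 30 mg | Ratio at 100 mg | Implied ratio at 300 mg |
|---|---|---|---|---|
| 0.7 | 139 | 0.50 | 0.30 | 0.18 |
| 1 | 46 | 0.50 | 0.30 | 0.22 |
| 3 | 27.5 | 0.50 | 0.30 | 0.29 |

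Every slope reproduces the observed doses. What varies is ED50 and the prediction at 300 mg, a dose with no Week 36 visit. Section 9.4.2.3 does not list curve parameters among its outputs.

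**Step 3: precision.** The 95% factor for one dose against concurrent placebo is exp(t × SD × √(1/n₁ + 1/n₂)), with n₁ + n₂ − 2 degrees of freedom.

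| Contrast | Factor at SD 0.5 | SD 0.4 to 0.6 |
|---|---|---|
| Week 26, 6 v 12 | exp(2.120 × 0.5 × 0.500) = 1.70 | 1.53 to 1.89 |
| Week 26, 9 v 12 | 1.59 | 1.45 to 1.74 |
| Week 32, 6 v 6 | exp(2.228 × 0.5 × 0.577) = 1.90 | 1.67 to 2.16 |
| Week 36, 9 v 6 | exp(2.160 × 0.5 × 0.527) = 1.77 | 1.58 to 1.98 |
| Week 40, 6 v 2 | exp(2.447 × 0.5 × 0.816) = 2.72 | 2.22 to 3.32 |

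Weeks 32 and 36 lose little. Week 40 is clearly worse.

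**Step 4: what joint modelling would recover at Week 40.** This uses generalised least squares on the placebo data, compound symmetry, an assumed within-person correlation of 0.3, 0.5 or 0.7, 16 degrees of freedom and SD 0.5. With a free placebo mean at each visit, the effective placebo n is 2.2, 2.7 or 3.7 and the factor 2.29, 2.17 or 2.01. With a linear placebo trend after Week 26, the effective n is 6.5, 7.3 or 8.6 and the factor 1.82, 1.79 or 1.76. The larger gain is bought by assuming the shape of the placebo course.

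**The case for a change.** The strongest case for a change is that an analysis plan cannot create shared visits: the schedule is fixed here. Late recovery at the top doses is a declared interest. Section 4.6 predicts that even 2 mg returns to half its maximum effect only around Day 150, so much of the recovery at higher doses may fall after Week 26. There, 100 and 300 mg can be compared only through a model for time. Section 9.4.2.3 names none, and the population model in Section 9.4.3 is exploratory and conditional on the data. An added Week 32 eosinophil count for the 30 and 100 mg cohorts would give one late visit with all five doses and 12 placebo participants, and Section 7 lets time points be added by Note to File.

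Part of this stands. After Week 26 a difference between 100 and 300 mg cannot be separated from time without a model, and the Week 40 placebo comparison is thin. But the extra visit costs 24 clinic attendances (one for each of 24 participants), departs from a schedule deliberately fitted to predicted duration of action, comes only six weeks after a visit that already has every dose, and leaves Weeks 36 and 40 as they are. Withholding Emax-based results at Weeks 36 and 40 would go too far: it would discard contrasts that the data support. As for a time model, the indirect-response approach suggested in Section 9.4.3 can use all doses and visits together.

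**Conclusion.** No change to the protocol follows. The visit counts, the rank shortfall at Weeks 36 and 40 and the 6 v 2 comparison are all correct, but the harm is narrower than it first appears. Estimates for observed doses stay data-driven. Only curve parameters and predictions for doses absent from a visit depend on the prior, and only if the model is fitted separately by visit, which the protocol does not say. Joint or by-visit fitting and the pooling of placebo are details the analysis plan normally settles, and an unsuitable fit already has a fallback.

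The remaining cost is precision at one visit in one cohort: about ×/÷ 2.7 at Week 40 against ×/÷ 1.7 at Week 26 for 300 mg, under an assumed log-scale SD of 0.5 (2.2 to 3.3 against 1.5 to 1.9 for SD 0.4 to 0.6). Longitudinal modelling could bring Week 40 to roughly 1.8 to 2.3, depending on the assumed correlation and placebo shape. This is a secondary endpoint in a study with no formal hypotheses (Section 9.1) and a feasibility-based size (Section 9.2), and the 6-month question is served by Week 26. Analysts should read stand-alone late curves with care, as they would anyway.

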3. OBJECTIVES AND ENDPOINTS

Objectives	Endpoints
Primary	

 To assess the safety and tolerability of ascending single subcutaneous doses of GSK3511294 in participants with mild to moderate asthma 	
 Adverse events, serious adverse events, including systemic reactions and local injection site reactions Vital signs, ECGs, laboratory safety data – including liver and renal chemistry, high sensitivity C-reactive protein (hsCRP), and complement (C3 and C4)
Secondary	

 To evaluate the plasma pharmacokinetics of ascending single subcutaneous doses of GSK3511294 in participants with mild to moderate asthma To evaluate the dose response of blood eosinophil counts after ascending single subcutaneous doses of GSK3511294 in participants with mild to moderate asthma To assess the immunogenicity of GSK3511294 	
 Plasma pharmacokinetic parameters of GSK3511294 after single SC doses: AUC(0-∞), AUC(0-t), AUC(0-Week4), AUC(0-Week12), AUC(0-Week26), %AUCex, Cmax, tmax, tlast, CL/F, Vd/F, λz and t½ when assessable* Ratio to baseline in absolute blood eosinophil count Frequency and titers of binding ADAs to GSK3511294, before and after GSK3511294 administration
Exploratory	

 To assess the effect of single SC doses of GSK3511294 on lung function Serum total IL-5 following single SC doses of GSK3511294 To explore drug specific circulating immune complexes (CIC) after single SC doses of GSK3511294 To determine the effect of single SC doses of GSK3511294 on serum markers of asthma 	
 Change from baseline: forced expiratory volume in 1 second (FEV₁), forced vital capacity (FVC), peak expiratory flow (PEF) Serum total IL-5 levels Levels of CICs Change from baseline in asthma biomarkers

 To explore the PK/PD (blood eosinophil count) relationship after single SC doses of GSK3511294, if deemed appropriate 	
 GSK3511294 plasma concentration and blood eosinophil count for determination of Half maximal effective concentration (EC50) and maximum effect, if deemed appropriate

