- Follow up period: Participants will receive post-dose assessments during the in-patient period and attend the clinic for further post-dosing assessments, as outlined in the Time and Events Table (Section [7.1](#)). The follow-up period will be up to 40 weeks after dosing, and will be dose dependent, based on the predicted blood eosinophil profile. Participants in cohorts receiving 2 and 10 mg GSK3511294 will attend the clinic visits up to week 32, participants in cohorts receiving 30 mg and 100 mg will attend clinic visits up to week 36, and participants in cohorts receiving 300 mg will attend clinic visits up to week 40. (For unplanned dose levels, the duration of follow-up will be documented in Note to File.) The follow-up period for

any participant may be adjusted, if necessary, based on the anticipated duration of action or any safety concerns that may emerge during the study.

- Total duration: The scheduled maximum study duration for each participant who receives GSK3511294 or placebo will be up to 44 weeks (excluding pre-screening for blood eosinophils), including up to 28 days for screening, 4 days as an in-patient in the UK and 9 days in Germany ([Appendix 8](#)), and up to 40 weeks post-dosing to investigate the PD (blood eosinophil count) and safety profile.

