observed in relevant clinical populations. Therefore, simulations using a semi-mechanistic stochastic model were generated, incorporating the clearance (1.9-fold) and binding affinity (30-fold) improvements observed in monkeys, assuming the findings in monkey will translate into humans. The GSK3511294 simulations showed that a SC dose of GSK3511294 between 30–100 mg administered every 6 months could be a plausible therapeutic dose and dosing interval.

GSK3511294 starting dose: Given the clinical experience with IL-5 antagonism as a mechanism of action, a 2 mg SC dose of GSK3511294 is justified as a starting dose. The 2 mg SC dose is anticipated to correspond to an average maximum reduction in blood eosinophils of approximately 75% (occurring approximately 2 weeks post-dosing), with a return to approximately 50% of the maximum response at around 150 days post dose (Figure 4). This level of blood eosinophil reduction is less than that previously observed in the clinic with repeat dosing of mepolizumab that was well tolerated. Therefore, this sub-therapeutic GSK3511294 2 mg starting dose is anticipated to: be well tolerated; offer the possibility to evaluate the blood eosinophil return towards baseline over an operationally reasonable period of time; and hence the opportunity to assess the *in vivo* potency of GSK3511294 in human. The proposed starting dose of 2 mg is 3500-fold lower than the NOAEL dose established in the 26-week toxicity monkey study (dose expressed in mg/kg and assuming a 70 kg participant) and the predicted AUC 3470-fold lower than the exposure observed at the NOAEL dose (Table 1).

SAD increments: The proposed SC single doses to be investigated in this FTIH study are 2, 10, 30, 100 and 300 mg. These doses correspond to dose increments of 5-fold, 3-fold, 3.3-fold and 3-fold, respectively, and are considered acceptable considering the precedence of the IL-5 antagonism mechanism of action. Furthermore, sentinel participants are planned for each escalating dose level.

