5.4. Study Withdrawal Criteria

5.4.1. Individual participant withdrawal from the study

- A participant may withdraw from the study at any time at his/her own request, or may be withdrawn at any time at the discretion of the investigator for safety, behavioural, compliance or administrative reasons.
- If the participant withdraws consent for disclosure of future information, the sponsor may retain and continue to use any data collected before such a withdrawal of consent.
- If a participant withdraws from the study, he/she may request destruction of any samples taken and not tested, and the investigator must document this in the site study records.
- Procedures planned for the participant's last visit should be done at the time of early withdrawal. Furthermore, if a PK sample was not planned at the participant's last visit, it should be taken at early withdrawal.

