7.4. Pharmacokinetics

7.4.1. Blood Sample Collection

Blood samples for determination of GSK3511294 plasma concentration will be collected at the time points indicated in [Table 4](#).

The actual date and time of each blood sample collection will be recorded. The timing of PK samples may be altered and/or PK samples may be obtained at additional time points to ensure thorough PK monitoring.

Processing, storage and shipping procedures are provided in the appropriate lab manual.

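### Table 4 schedules no PK sample at the final Week 32 visit of the 2 mg and 10 mg cohorts, although eosinophils, ADA and CICs are drawn there (minor; cheap to close)

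*Protocol*

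**What the plan says.** - **Visits.** Section 4.2: "Participants in cohorts receiving 2 and 10 mg GSK3511294 will attend the clinic visits up to week 32". Note 5 to the Time and Events Table (section 7.1) lists their visits after Week 26 as "2 and 10 mg: Week 32 only". Week 32 is Day 225.
- **What is drawn at Week 32.** The Time and Events Table marks haematology, immunogenicity and CICs at that visit. Note 7 confirms the eosinophil count: "Blood eosinophils will be included in the haematology panel at all time points other than the pre-screen visit".
- **PK.** Section 7.4.1: "Blood samples for determination of GSK3511294 plasma concentration will be collected at the time points indicated in" Table 4. In that table ("Table 4 Pharmacokinetic sampling time points", section 7.1) the 2 mg and 10 mg row has 14 marks, the last at Day 183; Days 225, 253 and 281 are blank. The 30/100 mg row reaches Day 253 and the 300 mg row reaches Day 281, which are those cohorts' last visits. The German schedule refers to the same Table 4.
- **Use of the data.** Section 4.6 says the 2 mg starting dose should "offer the possibility to evaluate the blood eosinophil return towards baseline over an operationally reasonable period of time" and so allow potency in humans to be assessed. The exploratory PK/PD endpoint in section 3 is "GSK3511294 plasma concentration and blood eosinophil count for determination of Half maximal effective concentration (EC50) and maximum effect", if deemed appropriate.
- **Flexibility.** Sections 7 and 7.4.1 allow PK time points to be added; section 7 requires a Note to File, not an amendment. Section 5.4.1 adds for participants who leave early that "if a PK sample was not planned at the participant's last visit, it should be taken at early withdrawal".

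**The concern.** Low concentrations observed together with recovering eosinophil counts are informative about EC50. The risk table in section 4.7.1 expects eosinophils may still be reduced at the last visit, particularly at higher doses, so recovery data should come mainly from the low-dose cohorts. Those are the cohorts whose last eosinophil count has no same-day concentration. A concentration would also help in reading the last ADA result, because the protocol recognises that ADA can alter PK or PD. At stake is one observed concentration per active low-dose participant at the end of follow-up.

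**Working it through.** **Inputs (all from the Protocol)**
- Clearance 0.00465 L/h, bioavailability 75%, half-life about 37 days (section 4.6).
- Predicted AUC 323 µg·h/mL at 2 mg and 1613 µg·h/mL at 10 mg (Table 1).
- Half of the maximum eosinophil response regained at about 150 days after 2 mg (section 4.6).
- Cohorts 1 and 2: 8 participants each, 6 active and 2 placebo (section 4.2).

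**Reproducing the plan's figures.** AUC = F × dose / CL. At 2 mg, 0.75 × 2 / 0.00465 = 322.6; at 10 mg, 0.75 × 10 / 0.00465 = 1612.9. Both agree with Table 1.

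**Counting the schedule.** The low-dose row is pre-dose; 2, 8, 24 and 48 h; Days 5, 8, 15, 29, 57, 85, 127, 169 and 183. That is 14 samples, 13 of them post-dose. The Amendment 5 log shows the same 14 marks for this row, so a table-reading error is unlikely. (The higher-dose rows differ by one mark between the current table and the log, possibly through text extraction. The current table is used here, and the low-dose row is unaffected.)

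**Size of the gap.** 225 − 183 = 42 days, and 42/37 = 1.14 half-lives.

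**Predicted concentrations.** Assume a single-exponential tail, C(t) = AUC × k × exp(−kt), with k = ln 2 / 37 = 0.01873 per day and t = study day − 1. AUC per day is 323/24 = 13.46 µg·day/mL at 2 mg and 1613/24 = 67.2 µg·day/mL at 10 mg.

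| Study day | 2 mg (ng/mL) | 10 mg (ng/mL) | PK scheduled? |
|---|---|---|---|
| 127 | 23.8 | – | yes |
| 169 | 10.8 | – | yes |
| 183 | 8.3 | 41.6 | yes |
| 225 | 3.8 | 19.0 | no |

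Starting instead from the Table 1 Cmax (0.226 µg/mL at 2 mg), taken at day 10, gives 11.7, 9.0 and 4.1 ng/mL at 2 mg on Days 169, 183 and 225, and 20.5 ng/mL at 10 mg on Day 225. The picture is the same.

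**Effect on AUC.** The share of AUC beyond Day 183 is exp(−k × 182), about 3%.

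**Where half-recovery falls.** At 2 mg, about 150 days lies between the paired samples on Days 127 and 169, with another on Day 183. If 10 mg reaches half-recovery at the same concentration as 2 mg (an assumption), it does so ln 5 / k = 86 days later, at about 236 days. Week 32 (224 days) is then the nearest scheduled 10 mg observation. The 2 mg level at 150 days is about 15.2 ng/mL. The last scheduled 10 mg sample is 41.6/15.2 = 2.7 times that level, and a Day 225 sample would be 19.0/15.2 = 1.25 times.

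**The case against.** The schedule looks considered. Amendment 5 extended this row from Day 85 to Day 183, and Week 26 is also the last time-limited AUC endpoint. The planned PK/PD analysis uses population methods, for example an indirect response model (section 9.4.3). Such a model can use an eosinophil count without a same-day concentration, and each participant has 13 scheduled post-dose samples to support it. The ADA endpoint is frequency and titre, which needs no concentration, and ADA is already paired with PK at seven post-dose visits (Weeks 2 to 26). The range near 19 ng/mL is covered by paired 2 mg data on Days 127 and 169. At 2 mg, a Day 225 level near 4 ng/mL may not be quantifiable.

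All of this stands, and it limits the point to a minor one. What remains is that the 10 mg cohort has no observation of its own near its predicted half-recovery concentration. The permission to add samples also schedules nothing until it is used.

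A reader might infer more, and the documents do not support it:
- **That the secondary PK endpoints or the purpose of the 2 mg dose are compromised.** About 3% of AUC is at issue, and the 2 mg half-recovery is bracketed by paired samples.
- **That section 5.4.1 makes the plan inconsistent, because a participant who drops out gives a final PK sample and a completer does not.** The rule recovers one concentration from someone who may miss later scheduled samples; a completer has all 14. Its wording allows for last visits without PK.

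**Conclusion.** The omission is real, and its consequence is minor. The loss is an observed concentration for the final eosinophil and ADA results of 12 active participants, and it matters mainly for the six on 10 mg. The size rests on the protocol's predicted PK, a single-exponential tail and, for the 10 mg recovery time, the same effect concentration at both doses. ADA that speeds clearance would make Day 225 harder to predict from earlier samples, but the protocol gives no human data on how often this occurs. The assay limit is not stated. What can be said is that the predicted 10 mg level on Day 225 is higher than the 2 mg levels the plan already samples on Days 169 and 183, so it should be no harder to measure than those.

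**What to change.** Add a mark under Day 225 in the 2 mg and 10 mg row of Table 4, so that every planned cohort has a PK sample at its last visit. A Note to File under section 7 would also be enough. The tube should be drawn from all 16 participants, placebo included, so that sampling does not reveal allocation. The cost is one tube per participant at an existing blood draw, plus assay. Some 2 mg results may be below the limit of quantification. If the sponsor prefers to keep Day 183 as the last sample, one sentence giving the reason would settle the point.
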